20.10 Appendix 10: Hepatitis B and Hepatitis C Serologic Testing Details

Hepatitis B Testing Details

HBsAg positive subjects are excluded. However, in case of past infections/vaccinations in order to qualify, the subject's testing status needs to align with the information in Table 6.

Table 6 Hepatitis B Testing

| Past Infection (Resolved) | | Or | Vaccinated | |
|---------------------------|----------|-----------|------------|----------|
| HBsAg | Negative | | HBsAg | Negative |
| Anti-HBc | Positive | | Anti-HBc | Negative |
| Anti-HBs | Positive | | Anti-HBs | Positive |

Hepatitis C Testing Details

Anti-HCV positive and HCV-RNA positive are excluded. In order to qualify for enrollment, the subject's testing status needs to align with the information in Table 7.

Table 7 Hepatitis C Testing

| Non-Reactive | | Or | Past Infection (Resolved) | |
|--------------|----------|-----------|---------------------------|----------|
| Anti- HCV | Negative | | Anti- HCV | Positive |
| | | | HCV RNA | Negative |

20.11 Appendix 11: Open Label Extension Period (Optional)

20.11.1 Summary of the Open-Label Extended Dosing Period

Subjects who complete the double-blind, placebo-controlled treatment period (including the Day 99 study visit) and meet the open-label extended dosing eligibility criteria will be given the option to receive 7 doses of 300 mg lirentelimab SC through the open-label extended (OLE) dosing period.

On Day 99 (± 5 days) of the double-blind period, eligible subjects participating in the OLE period will begin following the OLE Schedule of Events ([Table 8](#)) and will no longer follow the double-blind period Schedule of Events ([Table 1](#)). If OLE Day 1 is completed on the same day as Day 99, already completed assessments (for Day 99) do not need to be repeated (for OLE Day 1), as long as they are performed within time frames noted in the [Table 8](#) notes.

The OLE dosing period is summarized as follows:

- The Investigator will evaluate whether the subject is eligible for OLE. If eligible, the subject will be given the option to participate in the OLE period and receive 7 doses of open-label 300 mg lirentelimab SC administered every 2 weeks starting on Day 99 of the double-blind period, which will be considered Day 1 of the OLE period. OLE dosing may be delayed for up to 7 days after completion of the Day 99 visit.
- On Day 99, after completing all Day 99 assessments, eligible subjects who choose to participate in the OLE period will begin following the OLE Schedule of Events ([Table 8](#)).
- Day 1 of the OLE can occur up to 7 days following Day 99 of the double-blind period. In case Day 1 of the OLE is not the same as Day 99 of the double-blind period, applicable subjects (women of childbearing potential) will have a urine dipstick pregnancy test.
- After OLE Day 1, subsequent doses will be given on OLE Days 15, 29, 43, 57, 71, and 85 (± 5 days).
- All differential blood counts will be blinded to the Sponsor and the site until after OLE Day 1 dosing.
- Subjects will remain at the site for at least 1 hour of observation after each dose. In the event of an IRR, the subject may require prolonged observation (>1 hour or until the symptoms resolve), as per Investigator discretion.
- Subjects will be followed for approximately 12 weeks after the last dose. Follow-up visits will occur on OLE Days 99, 141, and 169 (14, 56, and 84 [± 5] days) following the last dose of open-label study drug.

- If absolute lymphocyte and/or eosinophil counts have not recovered by the OLE Day 169 visit (last follow-up visit), subjects will return approximately every 28 days for extended follow-up until counts have recovered.

20.11.2 OLE Objective

The objective of the OLE period is to evaluate long-term safety and tolerability of up to 7 doses of open-label AK002 in subjects with AD. The Medical Monitor will review data from the OLE period relating to safety and tolerability throughout the course of OLE dosing.

20.11.3 OLE Eligibility Criteria

Following completion of the randomized, double-blind, placebo-controlled treatment period (including the Day 99 visit), eligible subjects will have the option to receive 7 doses of open-label 300 mg lirentelimab SC through participation in the OLE period.

Subjects who are not eligible or who choose not to participate in the OLE period, will remain in the double-blind study and continue to follow the double-blind period Schedule of Events ([Table 1](#)).

20.11.4 OLE Inclusion Criteria

Subjects are eligible to participate in the OLE period if all the following criteria are met:

- 1) Subject completed the randomized, double-blind, placebo-controlled treatment period, defined as having received all 7 SC injections of study drug (lirentelimab or placebo), and completed the Day 99 visit procedures.
- 2) Subject is willing and able to comply with the OLE period Schedule of Events ([Table 8](#)), including receiving the first open-label 300 mg lirentelimab SC at the Day 99 visit which is 14 days following the last dose of study drug in the double-blind period or up to 7 days after the completion of the Day 99 visit.
- 3) Subject demonstrates continued eligibility per applicable inclusion criteria (Section [8.4](#)) and exclusion criteria (Section [8.5](#)) of the protocol. “Screening” in Section [13.1](#) refers only to the screening period completed prior to enrollment in the double-blind treatment period of the study and is not applicable to the OLE period.

20.11.5 OLE Exclusion Criteria

Subjects are not permitted to participate in the OLE period if any of the following criteria are met:

- 1) Previous administration of the study drug (lirentelimab or placebo) was poorly tolerated by the subject, in the opinion of the Investigator.
- 2) Any other reason that in the opinion of the Investigator or Medical Monitor makes the subject unsuitable for participation in the OLE period.

Acceptable documentation required to confirm inclusion and exclusion criteria will be further explained in the Study Reference Manual.

20.11.6 OLE Treatment

Formulation, storage, preparation, and administration of the open-label lirentelimab SC for OLE will be consistent with Section 10. of the protocol and the AK002-018 Pharmacy Manual.

The first OLE study drug administration of open-label 300 mg lirentelimab SC will be done on Day 99 of the double-blind period. This will be considered Day 1 of the OLE period. OLE dosing may be delayed for up to 7 days after the completion of the Day 99 visit. The subsequent injections will occur on Days 15, 29, 43, 57, 71, and 85 (± 5 days).

The subject will be observed for at least 1 hour (or longer as per Investigator discretion) after the end of the injection. In the event of an IRR, the subject may require prolonged observation (>1 hour or until symptoms resolve), as per Investigator discretion. Subjects will also be instructed to immediately contact the study doctor if any reactions occur after discharge.

20.11.7 OLE Procedures and Guidelines

The OLE period will be conducted in accordance with [Table 8](#) (Schedule of Assessments: Open-Label Extension Period) and the protocol. This includes prohibited medications, study drug preparation and administration, study assessment and procedure guidelines, AE reporting, withdrawal criteria and stopping rules, data collection and management, and ethical and regulatory requirements.

The Investigator will evaluate whether the subject is eligible for the OLE period. On Day 99, eligible subjects that choose to participate in the OLE period will begin following the OLE Schedule of Events ([Table 8](#)) and will receive the first open-label dose of lirentelimab.

Table 8 Study AK002-018 Schedule of Assessments: Open-Label Extension Period

| Assessment/Procedure Description | OLE Treatment Period (12 weeks) | | | | | | OLE Follow-Up Period ² (12 weeks) | | | |
|--|---|-------------------------|-------------------------|-------------------------|-------------------------|-------------------------|--|-------------------------|---|--------------------------|
| | OLE Day 1 (±5 days) OLE Baseline (Day 99-DB) | OLE Day 15 (±5 days) | OLE Day 29 (±5 days) | OLE Day 43 (±5 days) | OLE Day 57 (±5 days) | OLE Day 71 (±5 days) | OLE Day 85 (±5 days) | OLE Day 99 (±5 days) | OLE Day 141 (±5 days) | OLE Day 169 (±5 days) |
| Week 14 Dose 1 | Week 16 Dose 2 | Week 18 Dose 3 | Week 20 Dose 4 | Week 22 Dose 5 | Week 24 Dose 6 | Week 26 Dose 7 | Week 28 Follow-up 1 | Week 34 Follow-up 2 | Week 38 Follow-up 3/ EOS ³ | |
| Blood for PK ¹² | X ¹ | X | X | X | X | X | X | X | X | X |
| Blood for ADA ¹³ | X ¹ | | X | | | X | X | X | | X |
| Urine for dipstick pregnancy ¹⁴ | X ¹ | X | X | X | X | X | X | X | | |
| Urine for urinalysis ¹⁵ | X ¹ | | | | | | X | X | X | X |
| Eligibility assessment | X | | | | | | | | | |
| Study drug administration ¹⁶ | X | X | X | X | X | X | X | | | |
| Non-serious adverse events ¹⁷ | X ¹ | X | X | X | X | X | X | X | X | X |
| Serious adverse events ¹⁷ | X ¹ | X | X | X | X | X | X | X | X | X |
| ADA: Anti-lirentelimab antibody | | | | | | | PK: Pharmacokinetics | | | |
| CBC: Complete blood count | | | | | | | FSH: Follicle-stimulating hormone | | | |
| EASI: Eczema Area and Severity Index | | | | | | | hCG: Human Chorionic Gonadotropin | | | |
| | | | | | | | IgE: Immunoglobulin E | | | |
| | | | | | | | vlGA: Validated Investigator's Global Assessment | | | |
| | | | | | | | IRT: Interactive Response Technology | | | |
| | | | | | | | EOS: End of Study | | | |
| | | | | | | | | | | |

Table 8 Notes

- If OLE Day 1 takes place the same day as Day 99, the following assessments should only be done under Day 99 and not duplicated under OLE Day 1: prior/concomitant medications, body weight, symptom-directed physical exam (if applicable), vIGA, EASI, Atopic Conditions Questionnaire, blood for IGE, Chemistry, CBC, PK, and ADA, urine for dipstick pregnancy test (if applicable), and non-serious and serious adverse events. Blood draw and vital sign assessments must follow OLE Schedule of Events (as per below table notes).
- If absolute lymphocyte and/or eosinophil counts do not recover (to normal range or baseline levels) by OLE Day 169 or ET, extended follow-up visits are required every 14 (±5) days thereafter to monitor blood counts until they recover. Extended follow-up visits consist of blood collection for CBC with differential and collection of AESI and SAE.

Table 8 Notes cont.

- 3) EOS visits should be conducted 14 (± 5) days after the last dose of OLE or prior to this, if necessary, to ensure compliance with the visit. If a subject discontinues the study >14 days after last dose of study drug, the EOS visit should be conducted as soon as possible.
- 4) Body weight (in kg) will be measured on all dosing and follow-up days (14, 56, and 84 days after the last dose of study drug if ET).
- 5) Vital signs will be measured on all dosing and follow-up days (14, 56, and 84 days after the last dose of study drug if ET). On all dosing days: within 30 minutes predose, 15 (± 5) minutes after administration of study drug SC injection, and just prior to discharge. Additional vital sign measurements may be collected at the Investigator's discretion if an IRR occurs. Vital signs including systolic and diastolic blood pressure, pulse, body temperature, and respiratory rate will be measured after the subject has been at rest for ≥ 5 minutes and before any blood draws have been obtained (unless collected for an IRR).
- 6) A symptom-directed physical exam (including assessment of possible injection site reactions) will be performed by the Investigator or designee, as needed, if any symptoms are reported.
- 7) The vIGA, EAISI, [REDACTED] will be captured throughout the OLE period. Subjects entering into the OLE period of the study should continue completing the PRO daily. The PRO should be completed around the same time each day.
- 8) Subjects will be prompted to answer additional questions about symptoms related to asthma, allergic rhinitis, and allergic conjunctivitis (Atopic Conditions Questionnaire).
- 9) Blood samples for total serum IgE will be collected during predose on OLE Days 1, 57, and 85 and on follow-up Days 99, 141, and 169 or 14, 56, and 84 (± 5) days after last dose of study drug if ET.
- 10) Blood for chemistry will be obtained predose on dosing days and follow-up days (14, 56, and 84 [± 5] days after the last dose of study drug if ET).
- 11) Blood for CBC with differential will be obtained just prior to each SC injection, 1 hour (± 15 minutes) after the end of each SC injection as well as on all follow-up days (14, 56, and 84 [± 5] days after last dose if ET).
- 12) Blood for PK will be obtained predose on dosing days and on follow-up days (14, 56, and 84 days after the last dose of study drug if ET).
- 13) Blood for ADA will be collected predose on OLE dosing Days 1, 43, and 85 (± 5), on follow-up OLE Days 99 and 169 (14 and 84 [± 5] days after the last dose of study drug if ET. The ADA sample will also be collected any time an immunogenicity-related AE occurs.
- 14) Urine will be collected for dipstick pregnancy test on all dosing days and follow-up days (14, 28, 56, and 84 days after the last dose of study drug if ET) for all subjects of childbearing potential. Test kits will be supplied by the central laboratory. Tests will be completed on site and evaluated prior to each SC injection. If the Day 1 OLE visit does not occur on Day 99 of the double-blind period, then a dipstick urine pregnancy test will have to be done. Day 1 can occur up to 7 days after the Day 99 visit of the double-blind period.
- 15) Urine for standard urinalysis will be obtained on OLE Day 1 and follow-up Days 99 and 169 (14 and 84 days [± 5] if ET) and symptom-based, as necessary.
- 16) Subjects will remain under observation at the site for at least 1 hour after the end of each SC injection. In the event of an IRR, the subject may require prolonged observation (>1 hour or until the symptoms resolve), as per the Investigator's discretion. Subjects will also be instructed to immediately contact the study doctor if any reactions occur after discharge.

Table 8 Notes cont.

17) The capture of SAE, non-serious AE, and AESI will be captured through the OLE period until OLE Day 169 or ET. Adverse events will be assessed and recorded in the CRF of the AK002-018 OLE period database beginning from the start of the first open-label SC injection during the OLE Day 1 visit.

| | | 6.12.5 Physical Examination | 2 |
| | | 6.12.6 Analysis of Anti-Drug Antibodies | 2 |
| 7. | Vali | dation42 | 2 |
| 8. | Refe | rences4. | 3 |
| 9. | App | endices44 | 4 |
| | 9.1 | Appendix 1: Intercurrent Events and Definitions of Prohibited Medication Use and Rescue Medication/Treatment for AD Symptoms4 | |
| | 9.2 | Appendix 2: List of Tables, Figures, and Listings4 | 3 |

List of In-Text Tables

| Table 1 | Schedule of Assessments | |
|---------|-----------------------------|--|
| Table 2 | Terminology and Definitions | |
| Table 3 | | |
| Table 4 | Meaning of | |
| Table 5 | | |

List of Abbreviations

| AD | Atopic dermatitis |
|--------|---|
| ADA | Anti-drug antibody |
| ADaM | Analysis Data Model |
| AE | Adverse event |
| ANCOVA | Analysis of covariance |
| ATC | Anatomical Therapeutic Chemical (Classification System) |
| BLOQ | Below limit of quantification |
| BMI | Body mass index |
| CBC | Complete blood count |
| CDISC | Clinical Data Interchange Standards Consortium |
| СМН | Cochran-Mantel-Haenszel |
| CRF | Case Report Form |
| CRO | Contract Research Organization |
| CSR | Clinical study report |
| DM | Data management |
| ECG | Electrocardiogram |
| eCRF | electronic Case Report Form |
| EDC | Electronic Data Capture (system) |
| ET | Early Termination |
| FDA | Food and Drug Administration |
| ICE | Intercurrent events |
| ICH | International Conference on Harmonization |
| ICF | Informed Consent Form |
| IRT | Interactive Response Technology |
| ITT | Intent-to-treat (population) |
| LLN | Lower limit of normal |
| LLOQ | Lower limit of quantification |
| LSM | Least squares mean |
| MedDRA | Medical Dictionary for Regulatory Activities |
| mITT | Modified intent-to-treat (population) |
| MMRM | Mixed Model for Repeated Measures |
| NRI | Non-responder Imputation |

| p-value | Probability value |
|---------|---|
| PD | Pharmacodynamics |
| PE | Physical examination |
| РК | Pharmacokinetic(s) |
| PP | Per protocol (population) |
| PT | Preferred term |
| SAE | Serious adverse event |
| SAP | Statistical Analysis Plan |
| SAS | Statistical analysis system |
| SC | Subcutaneous |
| SD | Standard deviation |
| SE | Standard error(s) |
| SDTM | Study Data Tabulation Model |
| SOC | System organ class |
| TEAE | Treatment-emergent adverse event(s) |
| TEAESI | Treatment-emergent adverse event(s) of special interest |
| TESAE | Treatment-emergent serious adverse event(s) |
| TLF | Tables, listings, and figures |
| ULN | Upper limit of normal |
| WHO | World Health Organization |
| WHODD | World Health Organization Drug Dictionary |

Revision History

| Version Date | Version Number | Description |
|-------------------|-------------------|------------------|
| 25 July 2023 | 1 | Initial document |
| 18 September 2023 | 2 | Amendment 1 |

1. Introduction

Lirentelimab (AK002) Subcutaneous (SC) is being studied in subjects with moderate-to-severe atopic dermatitis inadequately controlled by topical treatments. Atopic dermatitis (AD) is a chronic pruritic inflammatory dermatitis that affects approximately 16.5 million (7.3%) adults in the US, of which around 6.6 million (40%) have moderate-to-severe disease.

The statistical analysis plan (SAP) describes *a priori* the data and variables to be summarized or analyzed, including specifications of the analytical methods to be performed. This SAP supersedes the statistical analysis methods described in the clinical protocol except for the standard pharmacokinetic (PK) data analyses. Significant deviations/changes from the planned analyses described in this SAP will be identified, with justification, in the appropriate section of the clinical study report (CSR). The SAP is based on Clinical Study Protocol AK002-018 Amendment 6, dated 08 September 2023, and the associated electronic case report form (eCRF).

2. Study Objectives

2.1 Primary Objective and Endpoint

The primary objective of the study is to assess the efficacy of lirentelimab SC in subjects with moderate-to-severe AD as assessed by the difference in the proportion of subjects who achieve at least 75 percent improvement from baseline in the Eczema Area and Severity Index (EASI-75) at Week 14 when compared with placebo.

In particular, the associated estimand for this objective is to measure the effect of therapy with lirentelimab SC as assessed by the proportion of subjects with EASI-75 response at Week 14 assuming treatment response disappears after subjects are rescued or discontinue from the study or treatment. See Sections 4.2.5 and 6.9.1 on how this estimand handles outcomes after the occurrence of any intercurrent event through non-responder imputation (NRI).

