The population targeted by the scientific question is defined via the inclusion and exclusion criteria as part of the study protocol. Subjects may be male or female and must have a clinical diagnosis of moderate-to-severe AD inadequately controlled by topical treatments as defined by the study inclusion criteria.

Variable (or Endpoint) to be Obtained for Each Subject that is Required to Address the Scientific Question

The primary endpoint to be obtained for each subject in this study to address the scientific question is the proportion of subjects who achieve EASI-75 at Week 14. For participants who drop out or initiate rescue or prohibited medication during the study, the outcome will be defined as “non-responder” after the date of such events.

Specification of How to Account for Intercurrent Events to Reflect the Scientific Question of Interest

The following intercurrent events will be anticipated and addressed:

- Premature discontinuation from the study
- Use of prohibited medications or rescue therapy during the study

For the analysis of the estimand, subjects who prematurely discontinue the randomized treatment or initiate any rescue or prohibited medication will be considered treatment non-responders at the designated time points after the start of such treatments.

7. Criteria for Evaluation

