4.2.4 Intercurrent Events

The events below are considered intercurrent events (ICE) confounding with the efficacy outcomes.

- Premature discontinuation from the double-blind portion of the study
- Use of prohibited medications during the study
- Use of rescue medication for symptoms of AD

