4.2.5 Strategy for Handling Intercurrent Events

For subjects who experienced an ICE of premature discontinuation from the double-blind portion of the study, efficacy outcome will be defined as "non-responder" for binary endpoints and will be set to missing for continuous endpoints from the point when that ICE occurs. An appropriate method for handling missing data through statistical modeling (e.g., multiple imputation [MI]) will be used.

For subjects that take prohibited medications during the double-blind portion of the study (see Appendix 1: Intercurrent Events and Definitions of Prohibited Medication Use and Rescue Medication/Treatment for AD Symptoms) for medically necessary reasons other than alleviating AD symptoms, the efficacy data will be handled as follows:

• The use of topical corticosteroids, topical calcineurin inhibitors, topical JAK inhibitors, topical PDE4 inhibitors or other prohibited topical medications for reasons other than for the treatment of AD for 5 or more days will result in all subsequent efficacy data being censored for purposes of analysis from the time of initiation of the prohibited therapy onwards. Use of prohibited topical therapies for a duration of less than 5 days will result in

all subsequent efficacy data being censored for purposes of analysis from the time of initiation of the prohibited therapy onwards only if the treatment occurs within 7 days of the Day 99 visit.

- The use of systemic corticosteroids for periods of 3 or more days or the use of depot injectable steroids for medical reasons other than the treatment of AD will result in all subsequent efficacy data being censored for purposes of analysis from the time of initiation of the prohibited therapy onwards. Use of systemic corticosteroids for a duration of less than 3 days will result in all subsequent efficacy data being censored for purposes of analysis from the time of initiation of the prohibited therapy onwards. Use of systemic corticosteroids for a duration of less than 3 days will result in all subsequent efficacy data being censored for purposes of analysis from the time of initiation of the prohibited therapy onwards if the treatment occurs within 28 days of the Day 99 visit.

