6.9.1 Analysis of Primary Efficacy Endpoint

The primary responder endpoint will be analyzed using the Cochran-Mantel-Haenszel test adjusted by baseline disease severity index [moderate (IGA=3) and severe (IGA=4)], prior biologic experience (biologic-naïve and biologic-exposed), and country (USA and Germany) at Week 14. A sample SAS code is as follows:

```
* COMPUTES CMH P-VALUE AND NEWCOMBE COMMON RISK DIFFERENCE ;
ods output CMH=PVAL(where=(althypothesis='Row Mean Scores Differ'))
CommonPdiff=DIFF;
proc freq data=ADEF ;
      tables DISEASE_INDEX*BIOLOGIC_EXPERIENCE*COUNTRY*TRTP*RESP /
cmh(MF) commonriskdiff
(cl=NEWCOMBE) ;
run ;
```

The Mantel-Fleiss (MF) criterion will be performed, and if it is not met while using the option CMH (MF) in SAS procedure PROC FREQ, analyses including each factor separately in CMH test will be conducted. Should assumption per the MF criterion not be satisfied, the comparison will be based on a Fisher's exact test after collapsing across levels of the stratification factor and country.

Below is an example of the SAS code for the Fisher's exact test:

```
* COMPUTE 95% EXACT CONFIDENCE INTERVAL FOR %RESPONSE FOR INDIVIDUAL
TREATMENT ;
ods output BinomialCLs=CL ;
proc freq data=ADEF ;
    table RESP / out=CNTS bin(cl=midp) ;
    by TRTP ;
run;
```

For the analysis described above, subjects who prematurely discontinue the randomized treatment or initiate any treatment adjustments (e.g., use of prohibited/rescue medication/rescue treatment for AD symptoms) will be handled as described below:

- If a subject withdraws from the study, this subject will be counted as a non-responder for the time points after withdrawal
- To account for the impact of prohibited/rescue medication/rescue treatment for AD symptoms on the efficacy effect: if rescue medication/rescue treatment for AD symptoms is used (see Appendix 1: Intercurrent Events and Definitions of Prohibited Medication Use and Rescue Medication/Treatment for AD Symptoms for definitions of ICE and listings of prohibited medications and rescue medications/therapies), the subject will be specified as a non-responder from the time the rescue medication/rescue treatment is used
- If the subject has the missing value at Week 14, it will be counted as a non-responder at Week 14

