6.12 Safety Analyses

6.12.1 Adverse Events

Safety assessments will be based mainly on the nature, frequency, relationship, and severity of adverse events (AE). The AE will be coded by primary System Organ Class (SOC) and Preferred Term (PT) according to MedDRA (version 21.0). The treatment-emergent adverse events (TEAE) will be summarized by the number and percentage (n and %) of subjects in each SOC and PT.

For summaries by relationship to study drug, "possibly related" will be combined with "related", and "unlikely/remotely related" will be combined with "not related." When multiple AE are reported with the same PT, the AE of the strongest relation to study drug will be included in the summary by relationship, and the AE of the most severe grade will be included in the summary by severity table.

The following AE incidence tables will be presented.

- Overview of TEAE to include
 - Number (%) of subjects who reported at least 1 TEAE

- Number (%) of subjects who reported at least 1 treatment related TEAE
- Number (%) of subjects who reported at least 1 severe TEAE
- Number (%) of subjects who reported at least 1 serious TEAE
- Number (%) of subjects who reported at least 1 TEAE leading to treatment discontinuation
- Number (%) of subjects who reported at least 1 TEAE leading to study discontinuation
- Number (%) of subjects who reported at least 1 TEAE of special interest (TEAESI)
- TEAE by PT sorted by decreasing order of subject incidence in the combined treatment group
- TEAE by SOC and PT in alphabetical order
- TEAE by SOC, PT, and maximum severity
- TEAE by SOC, PT, and strongest relationship to study drug
- TEAE leading to treatment discontinuation by SOC and PT, if warranted by sample size
- TEAE leading to study discontinuation by SOC and PT, if warranted by sample size
- Serious TEAE by SOC and PT, if warranted by sample size
- TEAESI by SOC and PT

All AE will be listed with onset/stop day, relationship to study drug, severity, action taken, and outcome. Pertinent subject information including treatment group and demographics will also be included.

Separate listings will be provided for TEAE leading to study discontinuation, TEAE of special interest, and treatment-emergent serious AE (TESAE).

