9.2 Appendix 2: List of Tables, Figures, and Listings

9.1 Appendix 1: Intercurrent Events and Definitions of Prohibited Medication Use and Rescue Medication/Treatment for AD Symptoms

Intercurrent events (ICE) are considered to potentially confound the efficacy outcomes of the study and are defined as follows:

- Premature discontinuation from the double-blind portion of the study for any reason
- Use of prohibited medications during the study
- Use of rescue medication/therapy for symptoms of AD

Prohibited medications are defined as therapies that should not be taken during the course of the study either because of a potential impact on the assessment of efficacy and/or subject safety. Rescue medications/treatments are defined as any therapy or treatment taken during the course of the study for the specific purpose of alleviating AD symptoms that may have an impact on the assessment of efficacy and includes: (1) topical medications (including TCS, TCI and crisaborole), (2) systemic medications (including systemic corticosteroids, immunosuppressant, and biologics), and (3) treatments known to impact AD.

The following provides the details of the prohibited medications/therapies for this study:

1) Prohibited medications where route of administration includes topical/transdermal

Topical Corticosteroids (TCS): ATC code D07 High Potency TCS: ATC codes D07AC or D07AD Low or moderate potency TCS: ATC code D07, excluding D07AC or D07AD
Topical calcineurin inhibitors (TCI): where Preferred Term includes tacrolimus, pimecrolimus
Coal tar: ATC code D05AA
Phosphodiesterase-4 Inhibitors (PDEi): ATC code L04AA32 where Preferred Term includes Crisaborole: ATC code D11AH, roflumilast (no topical ATC code) or apremilast gel

2) Prohibited systemic medications (including systemic corticosteroids, immunosuppressants, immunomodulators, and biologics)

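### Primary estimand treats stopping study drug as loss of response, but the SAP's intercurrent-event lists and Week 14 scoring rules leave it out, so a subject off drug can count as an EASI-75 responder

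*SAP*

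**What the plan says.** SAP 2.1 states the primary estimand as the effect on EASI-75 at Week 14 "assuming treatment response disappears after subjects are rescued or discontinue from the study or treatment", applied through non-responder imputation, and refers to SAP 4.2.5 and 6.9.1 for the mechanics.

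SAP 4.2.4 lists three intercurrent events: "Premature discontinuation from the double-blind portion of the study", prohibited medication, and rescue medication. SAP 4.2.5 ties its discontinuation rule to "an ICE of premature discontinuation from the double-blind portion of the study". SAP Appendix 1 repeats the three events, the first as "Premature discontinuation from the double-blind portion of the study for any reason".

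The lead-in in SAP 6.9.1 names subjects who stop randomized treatment early and says that the bullets describe their handling. The first bullet reads "If a subject withdraws from the study, this subject will be counted as a non-responder for the time points after withdrawal". The second covers rescue and the third a missing Week 14 value.

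Protocol Section 6 says that "subjects who prematurely discontinue the randomized treatment or initiate any rescue or prohibited medication will be considered treatment non-responders", although its own event list mentions only leaving the study and prohibited or rescue therapy. SAP Section 1 states: "This SAP supersedes the statistical analysis methods described in the clinical protocol", with an exception only for standard PK analyses.

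For continuous endpoints, SAP 6.9.2 explicitly censors data after permanent discontinuation of study drug.

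**The concern.** The estimand and the rules that a programmer would implement disagree about who is a primary-endpoint responder. Someone who stops study drug, remains in follow-up as Protocol 15.2 encourages, takes no rescue or prohibited medication and has an EASI in the Week 14 window meets none of the three 6.9.1 bullets. Read literally, the observed EASI-75 status stands. The binary IGA endpoint inherits the gap because it is analysed in the same way as the primary. Percent change in EASI does not inherit it, so one EASI value can count as a response in the primary analysis and be censored in the first secondary analysis.

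If this is left open, the reading could be chosen with results known, and the primary test gates both secondary endpoints (SAP 5.8). The per-protocol analysis does not settle the matter: it removes everyone without all 7 injections instead of scoring them as non-responders.

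**Working it through.** **Is stopping drug the same as leaving the study?** The documents keep the two apart.

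- SAP 6.12.1 tabulates "Number (%) of subjects who reported at least 1 TEAE leading to treatment discontinuation" on a separate line from events leading to study discontinuation.
- Protocol 14.7.5 records action on study drug separately from action on study participation.
- Protocol 15.1 defines double-blind completion by visits attended, not doses received.
- Protocol 15.2 encourages subjects who stop drug to remain on study.

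**Does anything else close the gap?** The blinded adjudication in SAP 4.2.5 covers only prohibited and rescue medication. The mITT population keeps anyone with at least one injection, apart from key eligibility violations. All Subjects All Data (SAP 6.1.3) is defined by who is included and is silent on values after discontinuation.

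**Which off-drug subjects have a Week 14 value?** The Week 14 window is Day 99 ± 5, that is Days 94-104 (SAP 5.2 and Table 1). If visits follow 14, 56 and 84 days after the last dose, the nominal days are:

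| Last dose (day) | +14 | +56 | +84 | In Days 94-104? |
|---|---|---|---|---|
| 1 | 15 | 57 | 85 | no |
| 15 | 29 | 71 | 99 | yes |
| 29 | 43 | 85 | 113 | no |
| 43 | 57 | 99 | 127 | yes |
| 57 | 71 | 113 | 141 | no |
| 71 | 85 | 127 | 155 | no |

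So 2 of 6 stopping points reach the window on nominal days. With the ±5-day windows, last doses scheduled for Day 29, 57 or 71 can also do so. A last dose on Day 1 cannot through these visits.

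Three readings are possible:

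1. Off-drug subjects follow the calendar visits (Days 99, 141, 169), and all who attend Day 99 are scored on observed data.
2. They follow only the post-last-dose visits. Those with no value in the window become non-responders through the missing-value bullet.
3. They are classed as discontinued from the study, as Protocol 9.3 words it for some rescued subjects who are still followed. They are then already non-responders.

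**The plan's own figure.** For 44% versus 15%, two-sided 0.05, Fisher's exact test has 89.8% power at 55 per arm, which matches the stated 90%. The plan enrols 65 per arm. The planned difference is 44 − 15 = 29 points.

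**Size of the shift.** The documents give neither the proportion who stop drug and stay nor their response rate. Assume 2-10% of an arm and a response rate of 15-44% (the planned arm rates). The 10% dropout allowance is not the stop-and-stay rate.

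Shift in an arm = stay rate × response rate × share observed.

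- All observed: 0.02 × 0.15 = 0.3 points, up to 0.10 × 0.44 = 4.4 points. In subjects, 65 × 0.003 = 0.2 up to 65 × 0.044 = 2.9.
- One third observed (reading 2, nominal days, stops spread evenly over doses 1-6): 0.3/3 = 0.1 points, up to 4.4/3 = 1.5 points.
- Reading 3: zero.

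Shift in the treatment difference, all observed, with 44% response in active stoppers and 15% in placebo stoppers:

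- Equal stay rate s: s × (0.44 − 0.15) = +0.6, +1.5 and +2.9 points at 2%, 5% and 10%.
- 10% active, 2% placebo: 0.10 × 0.44 − 0.02 × 0.15 = +4.1 points.
- 2% active, 10% placebo: 0.02 × 0.44 − 0.10 × 0.15 = −0.6 points.

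**Can one subject matter?** With 65 per arm and 10 placebo responders, moving from 19 to 20 active responders takes the unstratified chi-square p from 0.058 to 0.037. With Fisher's test the crossing is from 20 to 21 (0.060 to 0.039).

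**The case against.** The intent is visible. SAP 2.1 states the outcome, the 6.9.1 lead-in names treatment discontinuers, and Protocol Section 6 calls them non-responders. SAP 6.9.2 speaks of subjects who stop randomized treatment and then of time points after withdrawal, so the first 6.9.1 bullet could be read in the same loose sense. Precedence over the protocol matters only where the two documents conflict, and SAP 2.1 agrees with Protocol Section 6.

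The visit headings and Table 1 notes also favour the post-last-dose schedule for early stoppers, so many would have no Week 14 value and be non-responders anyway. The rates are assumptions, the affected group may be small or empty, and this is a Phase 2 proof-of-concept trial. Deleting the treatment clause from SAP 2.1 and Protocol Section 6 would also bring the estimand and the primary scoring into line.

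Much of this stands as a limit on size. The one-third share is an illustration, and the all-observed figures are an upper case. It does not repair the rule: the bullet specifies withdrawal from the study, and the documents elsewhere separate that from stopping drug. Visible intent shows that the operative text departs from the stated estimand. Deleting the clause is open to the sponsor as an estimand choice, but the primary endpoint would still differ from the censoring in 6.9.2.

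**Conclusion.** The concern holds. As written, the scoring rules permit a primary-endpoint responder whom the SAP's own estimand excludes, and they treat the same EASI value differently in the primary and first secondary endpoints. Under the assumed rates, the size runs from zero (reading 3) to 4.4 points in one arm, and from −0.6 to +4.1 points on the treatment difference in the cases shown. That would seldom overturn a true 29-point effect but could decide a close result. The textual finding is firm. The size is not, because it depends on rates the documents do not give and on a follow-up status they leave unclear.

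**What to change.** Before unblinding:

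- Add permanent discontinuation of randomized study drug to the intercurrent events in SAP 4.2.4, 4.2.5 and Appendix 1.
- Add a bullet to SAP 6.9.1: non-responder at all time points after permanent discontinuation of study drug, whether or not the subject remains in the study. This matches SAP 2.1, Protocol Section 6 and the censoring in SAP 6.9.2.
- If observed off-drug values are of interest, define them as a separate, named sensitivity analysis; All Subjects All Data does not currently do this.
- Reconcile Protocol 15.2, Table 1 note 2 and 13.12, so that it is clear which off-drug subjects have a Week 14 assessment.

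The cost is a few lines of SAP wording, plus the reconciliation of those protocol passages. No new data are needed and the planned sample size is unchanged. Response rates may fall slightly in one or both arms. With 65 per arm, on-drug rates of 44% and 15%, and equal off-drug shares, power is 94.7% (5% off drug) or 93.0% (10%) when these subjects are non-responders, against 96.0% if observed values at the same rates were kept (pooled normal approximation). All three exceed the planned 90%.
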